1.3. Schedules of Activities

Table 1: Schedule of Activities—Pre-screening Period and Screening Period (All Cohorts)

	Pre-screening Visit ^a	Pre-screening Period ^a	Screening Visit ^b	Screening Period ^b
Study Week	NA	Weekly Visits	Up to 6 weeks before Study Drug Administration	Weekly after Screening Visit until Study Drug Administration
Study Day	NA	NA	May be from Day -42 to Study Drug Administration Day	May be from Day -42 to Study Drug Administration Day
Visit Window (Days)	NA	±3	NA	±3
Study Procedures				
Informed consent/assent ^c	X		X	
I/E criteria	X ^d		X	
Demographics			X	
Medical history ^d			X	
Documentation of HLA typing ^e			X	
Prior and concomitant medications including			X	X

	Pre-screening Visit ^a	Pre-screening Period ^a	Screening Visit ^b	Screening Period ^b
Study Week	NA	Weekly Visits	Up to 6 weeks before Study Drug Administration	Weekly after Screening Visit until Study Drug Administration
Study Day	NA	NA	May be from Day -42 to Study Drug Administration Day	May be from Day -42 to Study Drug Administration Day
Visit Window (Days)	NA	±3	NA	±3
conditioning regimen for HCT				
Adverse events ^f			X	X
Complete physical examination			X	
Weight and height ^g			X	
Vital signs ^h			X	
12-lead ECG			X	
Clinical labs ⁱ			X	
Pregnancy test ^j			X	
Testing for HIV, HCV, HBV ^k			X	

	Pre-screening Visit ^a	Pre-screening Period ^a	Screening Visit ^b	Screening Period ^b
Study Week	NA	Weekly Visits	Up to 6 weeks before Study Drug Administration	Weekly after Screening Visit until Study Drug Administration
Study Day	NA	NA	May be from Day -42 to Study Drug Administration Day	May be from Day -42 to Study Drug Administration Day
Visit Window (Days)	NA	±3	NA	±3
BKV, AdV, CMV, JCV, EBV, and HHV-6 viral load ^l	X	X	X	X ^m

Abbreviations: AdV = adenovirus; ALT = alanine aminotransferase; AST = aspartate aminotransferase; ; β-HCG = beta human chorionic gonadotropin; BKV = BK virus; CBC = complete blood count; CMV = cytomegalovirus; EBV = Epstein-Barr virus; ECG = electrocardiogram; GGT = gamma-glutamyltransferase; HBV = hepatitis B virus; HCV = hepatitis C virus; HIV = human immunodeficiency virus; HHV-6 = human herpesvirus 6; HLA = human leukocyte antigen; I/E = inclusion and exclusion; JCV = JC virus; LFT = liver function test; NA = not applicable; PBMCs = peripheral blood mononuclear cells

Note: Visits may be done via a home health visit as agreed with the Sponsor. Please see the Study Manual for more information.

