^a Adult patients and pediatric patients ≥12 years old may participate in an optional pre-screening period that may begin up to 4 weeks prior to administration of conditioning for HCT and continue until there is a decision on whether to screen for the study. Viremia testing during pre-screening will begin after HCT and will continue weekly, if possible. Pre- screening is not required for eligibility.

^b The Screening Visit could occur any time between the day of HCT and up to 42 (+7) days post-HCT. When this visit occurs during this time period may vary by patient depending upon when the decision is made to participate in the study.

^c Prior to conducting any study-related activities, written informed consent/assent to participate in the study must be provided by the patient and/or patient's guardian. The ICF for the pre-screening period is separate from the ICF that is signed at Screening Visit for study participation.

^d To include CMV sero status of both patient and HCT donor

^e The HLA type of the patient and their HCT cell donor(s) will be obtained from the medical record.

^f Adverse events will be monitored and documented from signing of the ICF for study participation until study participation is complete.

^g Height and weight will be measured at screening. At later assessments during the Treatment Period, only weight will be assessed.

^h Includes body temperature, blood pressure, heart rate, O₂ saturation, and respiration rate and will be measured after resting for 5 minutes.

ⁱ Clinical laboratory assessments collected as part of standard of care may be used to fulfill these requirements. CBC must include differential and LFTs must include alkaline phosphatase, bilirubin (total and direct), GGT, AST, and ALT. Urinalysis must be performed. Laboratory safety evaluations (hematology, chemistry, and urinalysis) specified in [Section 8.4.4](#) will be performed prior to study therapy initiation. These samples will be sent to the appropriate central laboratory(ies) following the procedure(s) described in the study manual(s).

^j For female patients, at Screening a β-HCG blood test will be performed. A urine pregnancy test will also be performed at the site prior to study therapy initiation (SoA for Treatment Period, [Table 2](#)).

^k Serum will be screened for HIV, HBV, and HCV antibodies with reflex nucleic acid testing of plasma. Medical records of previous testing in the last 3-6 months may be used.

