Time Period	Treatment Assignment	Study Drug Administration Day	Treatment Period													
			Wk 1	Wk 2	Wk 3	Wk 4	Wk 5	Wk 6	Wk 7	Wk 8	Wk 9	Wk 10	Wk 11	Wk 12	Wk 13	Wk 14
Study Day		1 ^a	8	14	21	28	35	42	49	56	63	70	77	84	91	98
Visit Window (Days)		NA	±3	±5	±3	±5	±3	±5	±3	±5	±3	±5	±3	±5	±3	±3
Study Procedures																
Quality of Life (FACT-BMT, EQ-5D-5L, EQ-5D-Y, EQ-5D-Y Proxy Version 1) ^b		X												X		X

Abbreviations: AdV = adenovirus; ALT = alanine aminotransferase; AST = aspartate aminotransferase; ; β-HCG = beta human chorionic gonadotropin; BKV = BK virus; CBC = complete blood count; CMV = cytomegalovirus; EBV = Epstein-Barr virus; ECG = electrocardiogram; ET = Early Termination Visit; GGT = gamma-glutamyl transferase; GVHD = graft versus host disease; HBV = hepatitis B virus; HCV = hepatitis C virus; HIV = human immunodeficiency virus; HHV-6 = human herpesvirus 6; I/E = inclusion and exclusion; IVIG = intravenous immunoglobulin; JCV = JC virus; LFT = liver function test; NA = not applicable; PBMC = peripheral blood mononuclear cell; SoA = Schedule of Activities; VST = virus-specific T cell; Wk = week

Note: Visits may be done via a home health visit as agreed with the Sponsor. Please see the Study Manual for more information.

^a Unless noted otherwise, Day 1 procedures must be performed within 72 hours prior to study treatment administration.

^b Dosing day may be up to +7 days with Sponsor approval.

^c Adverse event monitoring should include the collection of all adverse events through the treatment period in all patients, including those who have discontinued study treatment but are continuing in the study. For patients who have discontinued, only drug-related SAEs and SAEs leading to death will be collected until Week 26.^d After treatment assignment, a targeted physical exam may be performed if a patient has any complaints. Post-HCT, the skin should be examined, even if the patient has no complaint, for evidence of rash/acute skin GVHD.

^e Includes body temperature, blood pressure, heart rate, O₂ saturation, and respiration rate and will be measured after resting for 5 minutes. After treatment assignment, vital signs should be performed during and after infusions and if targeted physical examination is performed.

^f Performed within 1 hour after study treatment administration and at the end of study or early termination visit, which are listed in the SoA for the Short-term Follow-up period (Table 3).

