^g Clinical laboratory assessments collected as part of standard of care may be used to fulfill these requirements. CBC must include differential and LFTs

must include alkaline phosphatase, bilirubin (direct and indirect); GGT, AST, and ALT. Urinalysis must be performed. Laboratory safety evaluations (hematology, chemistry, and urinalysis) specified in [Section 8.4.4](#) will be performed prior to study drug initiation. These samples will be sent to the appropriate central laboratory(ies) following the procedure(s) described in the study manual(s).

^h For female patients, a urine pregnancy test will be performed at the site prior to study therapy initiation. If the urine pregnancy test result is negative, the patient will be eligible for treatment assignment and the remainder of the Day 1 testing/procedures will be performed. If the urine pregnancy result is positive, the patient must not be assigned to treatment and should reflex to a β -HCG blood test before screen failing. A urine pregnancy test will be performed prior to each treatment for female patients who are of childbearing potential.

ⁱ Viral loads of AdV, BKV, CMV, JCV, and HHV-6 in plasma and of EBV in PCMBs will be measured. Additional post-infusion samples may be collected, as clinically indicated. If patient develops any clinically significant infection of AdV, BKV, CMV, EBV, HHV-6, or JCV at any point during the study periods, infection assessments should be followed prior to initiating standard of care therapy (see [Section 8.3](#)).

^j Patients in Cohort OL will be assigned to ALVR105. Patients in Cohorts A and B will be randomized to either ALVR105 or placebo based upon the last viral load assessed and within 7 days of randomization. Treatment assignment will be about 2 to 3 days before Day 1.

^k Patient peripheral blood mononuclear cells will be assessed for the presence of virus-reactive T cells using enzyme-linked immunospot.

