5.2. Exclusion Criteria

Patients who meet any of the following criteria will be excluded from participation in the study:

Medical Conditions

1. Has a history of AdV, BKV, CMV, EBV, HHV-6, and/or JCV end-organ disease within 6 months prior to treatment assignment
2. Has evidence of AdV, BKV, CMV, EBV, HHV-6, and/or JCV viremia for more than 3 viruses, from a central or local laboratory at any time during Screening prior to treatment assignment
3. Evidence of active Grade >2 acute GVHD (for additional information on acute GVHD grading and severity, see Appendix 5 [[Section 10.5](#)] or CRS Appendix 6 [[Section 10.6](#)], respectively).
4. Presence of non-minor uncontrolled or progressive bacterial or fungal infections (ie, evidence of bacteremia, fungemia, disseminated, and/or organ-specific infection not well controlled by present therapies)
5. Presence of progressive, uncontrolled viral infections with evidence of end organ disease
6. Known history or current (suspected) diagnosis requiring treatment of CRS associated with the administration of peptides, proteins, and/or antibodies
7. Evidence of encephalopathy at screening
8. Relapse of primary malignancy other than minimal residual disease.

Prior/Concomitant Therapy

9. Donor lymphocyte infusion performed within 21 days prior to randomization
10. Received within 7 days prior to treatment assignment any of the following: ganciclovir, valganciclovir, foscarnet, acyclovir (at doses >3200 mg PO per day or >25 mg/kg IV per day), valacyclovir (at doses >3000 mg PO per day), famciclovir (at doses >1500 mg PO per day)
11. Received any investigational antiviral agent/biologic therapy within 30 days prior to screening or plans to receive during the study any of the following: cidofovir, CMV hyper-immune globulin, or any investigational CMV antiviral agent/biologic therapy.
12. Ongoing therapy with high-dose systemic corticosteroids (ie, prednisone equivalent dose >0.5 mg/kg/day) within 7 days prior to screening
13. Prior therapy with antithymocyte globulin, alemtuzumab (Campath-1H), or other immunosuppressive T cell-targeted monoclonal antibodies within 28 days of treatment assignment
14. Receipt of mechanical ventilation of any type, within 1 month prior to the administration of ALVR105 (unless related to airway control)
15. Undergoing dialysis at any time during the screening period

Prior/Concurrent Clinical Study Experience

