6.8.1. Excluded Medications and/or Procedures

All patients may receive available supportive therapy with approved treatments. Investigators should try to maintain stable treatment to the extent possible.

Receipt of other investigational antiviral treatments (eg, brincidofovir or anti-BK virus monoclonal antibodies) within 28 days prior to randomization and throughout the duration of the study is prohibited.

Treatment with supportive regimen therapies, other intravesicular agents for the control of bleeding (including, but not limited to, aminocaproic acid), antispasmodics, treatment for pain control (including opioids), and blood product transfusion support are permitted. Analgesic use will be collected on a daily basis. Clinically available (ie, not investigational) antiviral agents prescribed for other infections are allowed. Use of cidofovir or brincidofovir (eg, for the treatment of AdV) must be discussed with the Medical Monitor prior to initiation. All instances of the use of any antiviral agents during the study will be recorded in the eCRF (including the drug name, dose, and

duration of treatment).

T cell ablative therapies, such as antithymocyte globulin, alemtuzumab (Campath-1H), or other immunosuppressive T cell-targeted monoclonal antibodies, are prohibited during the course of the study. Daily doses of corticosteroids exceeding 0.5 mg/kg prednisone (or equivalent) are prohibited during the course of the study. Should patients require medically a higher dose of steroids, no further study drug will be administered until the steroids are tapered to a dose equivalent of 0.5 mg/kg prednisone (or equivalent) or less.

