8.2.1. Definitions and Determination of Viremia

8.2.2. Viral Load

Samples for viral sequence/genotype will be collected on all patients as indicated in Section 1.3. Viral loads of AdV, BKV, CMV, HHV-6, and JCV in plasma and of EBV in PBMCs will be measured at times specified in Section 1.3. The results of any repeat analyses from screening must be available at the time of treatment assignment, with the exception of patients screened within 7 days of treatment assignment, who would not have more than 1 analysis. [REDACTED]

[REDACTED] Additional post-infusion samples may be collected, as clinically indicated. If patient develops any clinically significant infection of AdV, BKV, CMV, EBV, HHV-6, and JCV at any point during the study periods, infection assessments (Section 8.3) should be followed prior to initiating standard of care therapy.

[REDACTED] Resolution of viral infection will be defined as a return to normal range as defined by the assay used and complete resolution of clinical signs and symptoms as defined in the CAC charter.

Viral load will be quantitated using PCR assays.

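### Exclusion criterion 12 tests high-dose steroids only before screening, so a patient can be assigned while Section 6.8.1 temporarily bars dosing (minor, cheap to fix)

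*Protocol*

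**What the plan says.** Criterion 12 in Protocol Section 5.2 excludes "Ongoing therapy with high-dose systemic corticosteroids (ie, prednisone equivalent dose >0.5 mg/kg/day) within 7 days prior to screening". Its look-back ends at screening.

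Screening may be early. Table 1 footnote b (Section 1.3) says "The Screening Visit could occur any time between the day of HCT and up to 42 (+7) days post-HCT", and Table 1 gives its study day as "May be from Day -42 to Study Drug Administration Day". It may also be late: Section 8.2.2 provides for patients screened within 7 days of assignment. On the other side, Table 2 footnote j says "Treatment assignment will be about 2 to 3 days before Day 1".

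Once the patient is in the study, Section 6.8.1 applies the same threshold: "Daily doses of corticosteroids exceeding 0.5 mg/kg prednisone (or equivalent) are prohibited during the course of the study". If a higher dose is medically needed, "no further study drug will be administered until the steroids are tapered to a dose equivalent of 0.5 mg/kg prednisone" or less.

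Eligibility is confirmed on the day of assignment (Section 4.1), and the inclusion and exclusion criteria are reviewed on Day 1 (Tables 2 and 3). The first infusion must fall between 15 and 42 (+7) days after transplant (Section 8.1.3). The ITT population keeps every randomised patient, dosed or not (Section 9.3).

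**The concern.** The eligibility rule and the dosing rule share a threshold but apply it at different times. A patient who starts steroids above 0.5 mg/kg/day after the Screening Visit does not meet criterion 12. The checks at assignment and on Day 1 do not help, because they re-apply wording that looks back from screening. That patient can be assigned and then cannot be infused until the dose comes down.

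The first-infusion window is fixed relative to transplant, so waiting for a taper can delay the first dose or, late in the window, lose it. In a randomised cohort an undosed patient still counts in the ITT comparison and pulls the treatment difference towards zero.

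**Working it through.** **1. The plan's own screening length.** Six weeks × 7 = 42 days. SAP Section 3.1.1 has no Day 0, so Day -42 to Day 1 is also 42 days. As a cross-check, 6 + 14 + 12 = 32 weeks, the stated upper limit of participation.

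**2. Longest interval from screening to assignment.** Assignment is 2 to 3 days before Day 1, so 42 − 3 = 39 to 42 − 2 = 40 days. Counting a Day 0 would give 40 to 41. Transplant-day screening with assignment at day 42 (+7) would suggest 42 to 49 days, but the six-week screening limit binds first.

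**3. Other cases.**
- Screened within 7 days of assignment: 0 to 7 days untested.
- Screened on the day of transplant and assigned at the earliest permitted time, post-transplant day 15 (Section 5.1, criterion 5): 15 days untested. The 7-day look-back then covers only days up to the transplant.

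**4. Time left to taper after assignment.** Table 2 footnote b says "Dosing day may be up to +7 days with Sponsor approval"; I read this as the window for Day 1. The latest first dose is post-transplant day 42 + 7 = 49. For assignment on post-transplant day d:

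slack = min(2 to 3 + 7, 49 − d)

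- d = 15, 28 or 39: 9 to 10 days
- d = 40: 9 days
- d = 42: 7 days
- d = 46: 3 days
- d = 49: 0 days

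**5. How the nearby therapy criteria in Section 5.2 are anchored.**
- 9 (donor lymphocytes): randomisation.
- 10 (antivirals) and 13 (T cell-targeted agents): treatment assignment.
- 11 (investigational antivirals and others): screening, but it also reaches forward to planned use during the study.
- 12 (steroids): screening, with no forward reach.
- 14 (ventilation): administration of study drug.
- 15 (dialysis): the whole screening period.

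**6. ITT dilution, by assumption only.** If a fraction f in each randomised arm is never dosed for this reason, those patients contribute no difference between arms. The difference retained is 1 − f. With the variance taken as roughly unchanged, the sample size for the same power is multiplied by 1/(1 − f)².
- f = 0.01: 1/0.9801 = 1.02
- f = 0.02: 1/0.9604 = 1.04
- f = 0.05: 1/0.9025 = 1.11

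The documents give no rate of steroid use between screening and assignment, so these values of f are illustrative. Patients who are only delayed would dilute the comparison less.

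**The case against.** The strongest reply is that the plan largely handles this case elsewhere. Section 6.8.1 prohibits the dose during the study, and Section 4.1 counts screening as part of the study. Section 7.2 lists the need for a prohibited medication among the reasons for ending participation. Criterion 21 lets the investigator exclude a patient for a confounding therapy, and criterion 3 removes active acute GVHD above Grade 2. Medications are recorded throughout screening. Harm requires an investigator to assign a patient known to be on a prohibited dose instead of waiting within the transplant window. Holding and resuming drug is also a defensible way to manage steroids.

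Much of this stands, and it makes the scenario narrow. It does not close the gap. Criterion 21 and the Section 7.2 reason are discretionary, criterion 3 concerns GVHD grade and not steroid dose, and the stated consequence in 6.8.1 is withholding drug, not ineligibility.

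Three stronger readings are tempting but not supported:
- **That patients could be infused on high-dose steroids.** Section 6.8.1 prohibits this. Its hold speaks of further drug, so its application to the first infusion is inferred from the general prohibition. That is an ambiguity to clarify and does not permit dosing.
- **That criterion 12 alone is tied to screening.** Criterion 11 is too; the difference is its forward reach.
- **That Section 2.3.2 shows efficacy would be lost.** It reports that virus-specific T cells do not persist at methylprednisolone doses of 1 mg/kg/day or more. That explains why a hold exists; it does not show harm to a patient who is not infused.

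**Conclusion.** The gap is real and minor. On the visible text, criterion 12 leaves up to 39 to 40 days before assignment untested at the schedule maximum, and few or none for patients screened late. A patient in that gap can be assigned while temporarily not dosable, with between 0 and about 10 days of slack before the latest first dose.

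The limits are these. Frequency is unknown, and the sample-size factors of 1.02 to 1.11 rest on assumed rates. A reader might infer that the open-label results are affected. They are not: SAP Section 1 says those patients were enrolled, treated and followed, and SAP Section 3.2.2 restricts the analysis to patients who received the product. The benefit falls on later or randomised enrolment. Parts of Protocol Sections 4.1, 5.1 and 6.3 are redacted, and the text of Amendment 4, cited in the SAP, was not available, so either may already address the point.

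**What to change.** Make two wording changes, after checking whether the later amendment already contains them.

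1. In criterion 12, exclude systemic corticosteroids above 0.5 mg/kg/day prednisone equivalent that are ongoing at treatment assignment. The threshold is unchanged. The uncovered interval before assignment falls from a maximum of 39 to 40 days to 0.
2. In Section 6.8.1, state that the hold covers the first infusion as well as later ones. This deals with steroids started in the 2 to 3 days between assignment and Day 1.

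No new procedure is needed, since concomitant medications are already documented through screening (Table 1, Section 6.8.3). The cost is that a few patients are assigned later or fail screening. A 7-day look-back from assignment, as in criterion 10, is possible but is a trade-off: it would also exclude patients who tapered 1 to 6 days earlier and could be dosed under 6.8.1. The ongoing-at-assignment wording avoids that.

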5.3. Lifestyle Restrictions

This section is not applicable.

5.3.1. Caffeine, Alcohol, and Tobacco

This section is not applicable.

5.3.2. Activity

This section is not applicable.

5.4. Screen Failures

Screen failures are defined as participants who consent to participate in the clinical study but are not randomized into the clinical study. A minimal set of screen failure information is required to ensure transparent reporting of screen failure participants to meet the Consolidated Standards of Reporting Trials publishing requirements and to respond to queries from regulatory authorities. Minimal information includes demography, screen failure details, eligibility criteria, and any serious adverse events (SAEs).

Individuals who do not meet the criteria for participation in this study (screen failure) may be rescreened in consultation with the Medical Monitor.

6. STUDY INTERVENTION(S) AND CONCOMITANT THERAPY

Study intervention is defined as any investigational intervention(s), marketed product(s), placebo, or medical device(s) intended to be administered to a study participant according to the study protocol.

6.1. Study Intervention(s) Administered

[figure not shown]
ALVR105 is a third-party, donor-derived, “off-the-shelf,” VST product with specificity for BKV, AdV, CMV, EBV, and HHV-6 (with additional cross-reactive specificity for JCV) that is [REDACTED] and ready for immediate use. The Control Arm will receive IV infusions of [REDACTED] (without cells) as placebo.

Arm Name	Treatment (Cohort A and B and OL)	[REDACTED]
Intervention Name	ALVR105	[REDACTED]
Type	Drug	[REDACTED]
Dosage formulation	Ampule (Cryovial)	[REDACTED]
Unit dose strength(s)	[REDACTED]	[REDACTED]
Dosage Level(s)	[REDACTED] (<40 kg) or [REDACTED] (\geq 40 kg) dosed Q14D	[REDACTED]
Route of Administration	IV slow push [REDACTED]	[REDACTED]
Use	Experimental	[REDACTED]
Sourcing	Provided centrally by Sponsor	[REDACTED]
Packaging and Labeling	Study Intervention will be provided in cryovials. Each cryovial will be labeled as required per country requirement	[REDACTED]
Current/Former Name(s) or Alias(es)	ALVR105	[REDACTED]

